7.4. Blinding

This will be a double-blind study and the following will apply.

- The Investigator or treating physician may unblind a participant's treatment
 assignment only in the case of an emergency OR in the event of a serious
 medical condition when knowledge of the study treatment is essential for the
 appropriate clinical management or welfare of the participant as judged by the
 Investigator.
- Investigators have direct access to the participant's individual study treatment.

- In case of an emergency, the investigator has the sole responsibility for determining if unblinding of a participant's treatment assignment is warranted. Participant safety must always be the first consideration in making such a determination. If the investigator decides that unblinding is warranted, the investigator should make every effort to contact GSK prior to unblinding a participant's treatment assignment unless this could delay emergency treatment of the participant.
- If GSK personnel are not contacted before the unblinding, the Investigator must notify GSK within 24 hours after unblinding, but without revealing the treatment assignment of the unblinded participant, unless that information is important for the safety of participants currently in the study.
- The date and event or condition which led to the unblinding (i.e. the primary reason) will be recorded in source documentation and in the eCRF.

In the event of unblinding the Medical monitor/GSK team should be contacted to determine whether subject withdrawal is required. Should a participant's treatment assignment be unblinded and the Medical monitor/GSK team determine that the participant must be withdrawn from IP, the participant must be followed-up as per protocol until the completion of the Safety Follow-up assessments.

GSK's Global Clinical Safety and Pharmacovigilance (GCSP) staff may unblind the treatment assignment for any participant with an SAE. If the SAE requires that an expedited regulatory report be sent to one or more regulatory agencies, a copy of the report, identifying the participant's treatment assignment, may be sent to investigators in accordance with local regulations and/or GSK policy.

7.5. Preparation/Handling/Storage/Accountability

GSK3772847 a white to yellow, uniform lyophilized cake in a 5ml clear glass vial with 20mm closure sealed by red metal and yellow overseal. Each vial contains 100 mg of a lyophilised GSK3772847. When reconstituted with 2.0 mL of WFI, the final concentration of GSK3772847 is 50 mg/mL. Excipients include: sucrose, sodium phosphate buffer, and polysorbate 20 at a pH of 7.3. Vials contain no preservatives and thus are for single use. Vials must be stored 2° – 8°C, protected from light. Protection from light during preparation and administration is not required. Full details on specific 2° to 8°C storage temperature conditions, preparation and administration including requirements for filtration are provided separately.

Commercially available sterile normal saline will be used for dilution of study agent and will also serve as placebo for this study. Use of study agent sterile normal saline as placebo for injection provides an adequate comparator to broadly assess safety in early clinical development.

GSK3772847 must be prepared by an unblinded pharmacist or other appropriately licensed and authorized personnel and administered according to each participant's body weight at Screening (Visit 1). A different site staff member, who will be blinded to the treatment assignment, will administer the study agent. Aseptic procedures must be used during preparation and administration of the study agent. Diluted GSK3772847 at

volumes of 50 mL are to be administered by IV infusion over a period of at least 30 minutes using an in-line 0.22 micron filter. At least 30 mL of commercially available sterile normal saline will be used to flush diluted drug from the administration set to ensure full study agent administration.

Unblinded site staff will be responsible for receipt, storage, reconstitution, and labelling, and accountability of investigational product.

GSK3772847 should be inspected visually for particulate matter and discoloration prior to administration whenever solution and container permit. If visibly opaque particles, discoloration, or other foreign particles are observed, the solution should not be used.

Detailed instructions for storage conditions, dose preparation, and administration will be provided in the unblinded site staff reference manual. Required storage conditions and expiration date are indicated on the label.

- 1. The investigator or designee must confirm appropriate temperature conditions have been maintained during transit for all study treatment received and any discrepancies are reported and resolved before use of the study treatment.
- 2. Only participants enrolled in the study may receive study treatment and only authorized site staff may supply or administer study treatment. All study treatments must be stored in a secure, environmentally controlled, and monitored (manual or automated) area in accordance with the labeled storage conditions with access limited to the investigator and authorized site staff.
- 3. The investigator, institution, or the head of the medical institution (where applicable) is responsible for study treatment accountability, reconciliation, and record maintenance (ie, receipt, reconciliation, and final disposition records).
- 4. Further guidance and information for the final disposition of unused study treatment are provided in the Study Reference Manual or unblinded site staff reference manual.
- Under normal conditions of handling and administration, study treatment is not
 expected to pose significant safety risks to site staff. Take adequate precautions to
 avoid direct eye or skin contact and the generation of aerosols or mists. In the case of
 unintentional occupational exposure notify the monitor, Medical Monitor and/or
 GSK study contact.
- A Material Safety Data Sheet (MSDS)/equivalent document describing occupational hazards and recommended handling precautions either will be provided to the investigator, where this is required by local laws, or is available upon request from GSK.

Precaution will be taken to avoid direct contact with the study treatment. A Material Safety Data Sheet (MSDS) describing occupational hazards and recommended handling precautions will be provided to the investigator. In the case of unintentional occupational exposure notify the monitor, Medical Monitor and/or GSK study contact.

7.6. Treatment Compliance

- FP/Sal and FP during the run-in and treatment periods will be self-administered at home; compliance will be assessed via dose counter during the site visits and documented in the source documents and eCRF. A record of the number of doses on the DISKUS inhaler will be recorded in the eCRF. Treatment start and stop dates, including dates for treatment delays and/or dose reductions will also be recorded in the eCRF.
- The double blind IP will be intravenously administered to participants at the site. Administration will be documented in the source documents and reported in the eCRF.

7.7. Concomitant Therapy

All asthma medications used within approximately 12 weeks prior to screening and during the study (including the post-treatment period) should be recorded in the eCRF.

All non-asthma medications taken during the study (after randomization including post-treatment) and any changes to concomitant medications will be recorded in the eCRF. *Note: Study provided FP/Sal, FP, and albuterol/salbutamol should not be recorded in the ConMeds page of the eCRF.*

The minimum requirement is that the drug name, reason for use, dose (including unit e.g. mcg) and frequency, route and the dates of administration are to be recorded.

7.7.1. Permitted Non-asthma Medications

The following medications are permitted during the study:

- Medications for rhinitis (e.g., intranasal corticosteroids, antihistamines [including ocular and intranasal] but they are disallowed 48 hours prior to ECG measurements, cromolyn, nedocromil, nasal decongestants)
- Antibiotics for short term treatment of acute infections. Long term treatment with topical or ophthalmic antibiotics are permitted.
- Decongestants: Participants may take decongestants during the study, but these are disallowed for 24 hours prior to ECG measurements.
- Immunotherapy: Immunotherapy for the treatment of allergies is allowed during the study provided it was initiated 4 weeks prior to Visit 1 and participants remain in the maintenance phase for the duration of the study.
- Topical and ophthalmic corticosteroids.

7.7.2. Prohibited Medications and Non-Drug Therapies

Use of the medications listed below is not permitted during the study:

• Inhaled anti-cholinergics (e.g.tiotropium).

- ICS/LABA other than the study-provided FP/Sal.
- Inhaled Corticosteroids other than the study-provided FP.
- LABA other than the salmeterol component in the study-provided FP/Sal.

CONFIDENTIAL

- Biologics, e.g. Mepolizumab and Omalizumab.
- Potent CYP3A4 inhibitors, (e.g., ritonavir, ketoconazole, etc.)
- Anticonvulsants (barbiturates, hydantoins, and carbamazepine).
- Polycyclic antidepressants.
- Beta-adrenergic blocking agents.
- Phenothiazines.
- Monoamine oxidase (MAO) inhibitors.
- Live or attenuated vaccines (and up to 6 months after the last dose of blinded study treatment).
- Experimental anti-inflammatory drugs (non-biologics).
- Corticosteroids intramuscular, long acting depot, regular systemic (oral, parenteral, depot) corticosteroid.
- Methotrexate, troleandomycin, oral gold, cyclosporin, azathioprine.
- Theophylline.
- Chemotherapy and radiotherapy.

7.8. Treatment after the End of the Study

Participants will not receive any additional treatment from GSK after completion of the study or withdrawal of IP because other treatment options are available.

The Investigator is responsible for ensuring that consideration has been given to the post-study care of the participant's medical condition.

8. DISCONTINUATION CRITERIA

8.1. Discontinuation of Study Treatment

Participants that permanently stop study treatment are encouraged to remain in the study. Participants have the right to discontinue study treatment before the end of the study. A participant may also be asked to discontinue study treatment at the Investigator's discretion.

Participants who withdraw from study treatment prematurely (for any reason) should, where possible, continue to be followed-up until the completion of the Safety Follow-up assessments:

• For participants who discontinue IP early, but have not withdrawn consent to participate in the study, an early withdrawal (EW) visit will be performed 4 weeks after the last dose of blinded study treatment. These participants should continue in the study and complete all assessments at the remaining protocol-defined visits until their EW visit. Participants should resume regular treatment for their asthma, as determined by the investigator. Three Follow-up visits will then be performed 4, 8, and 12 weeks after the EW visit for safety assessments.

CONFIDENTIAL

• Participants who discontinue IP early and withdraw consent to participate in the study should complete as many assessments planned for the EW visit as possible.

If this is not possible, the Investigator must encourage the participant to participate in as much of the study as they are willing (or able) to.

A participant may be withdrawn from study treatment at any time. A reason for premature discontinuation of study treatment (e.g., AE, lack of efficacy [including loss of asthma control], protocol deviation, Investigator discretion, consent withdrawn etc.) must be captured in the eCRF.

A participant must be withdrawn from study treatment if any of the following stopping criteria are met:

- 1. Liver Chemistry: Meets any of the protocol-defined liver chemistry stopping criteria.
- 2. QTc: Meets any of the protocol-defined stopping criteria.
- 3. Pregnancy: Positive pregnancy test.
- 4. Participant meets at least one of the following criteria for 'loss of asthma control':
 - ACQ-5 score increase from baseline (measured at Visit 2) \geq 0.5 point.
 - Pre-bronchodilator FEV1 decrease from baseline (measured at Visit 2) >7.5 %.
 - Inability to continue inhaled corticosteroid titration which is assessed and determined by the investigator at any time point following randomization, including on scheduled clinic visits.
 - A clinically significant asthma exacerbation (requiring OCS and/or hospitalization).
- 5. Study treatment unblinded.

Note: In the event of unblinding the Medical monitor/GSK team should be contacted to determine whether subject withdrawal is required.

- 6. Abnormal Holter of Mobitz II AVB, complete AVB, sustained or non-sustained ventricular tachycardia (VT), paroxysmal supraventricular tachycardia (PSVT), new onset atrial fibrillation/flutter will be a withdrawal/stopping criterion. These findings on ECG or findings of myocardial ischemia will also result in withdrawal/stopping.
- 7. Hypersensitivity or anaphylactic reaction

[figure not shown]
8.1.1. Liver Chemistry Stopping Criteria

Liver chemistry stopping and increased monitoring criteria have been designed to assure participant safety and evaluate liver event etiology (in alignment with the Food and Drug Administration [FDA] premarketing clinical liver safety guidance). These protocol guidelines are in alignment with FDA premarketing clinical liver safety guidance:

http://www.fda.gov/downloads/Drugs/GuidanceComplianceRegulatoryInformation/Guidances/UCM174090.pdf.

Discontinuation of study treatment for abnormal liver tests should be considered by the investigator when a participant meets one of the conditions outlined in the algorithm or if the investigator believes that it is in the best interest of the participant.

Phase II Liver Chemistry Stopping and Increased Monitoring Algorithm

Liver Safety Required Actions and Follow up Assessments Section can be found in Appendix 7.

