8.1.2. QTc Stopping Criteria

- The QTc is the QT interval corrected for heart rate according to Bazett's formula (QTcB), Fridericia's formula (QTcF), and/or another method, machine-read or manually over-read. The *same* QT correction formula *must* be used for *each individual participant* to determine eligibility for and discontinuation from the study. This formula may not be changed or substituted once the participant has been enrolled.
- For example, if a participant is eligible for the protocol based on QTcB, then QTcB must be used for discontinuation of this individual participant as well.
- Once the QT correction formula has been chosen for a participant's eligibility, the *same formula* must continue to be used for that participant *for all QTc data being collected for data analysis*. Safety ECGs and other non-protocol specified ECGs are an exception.

• The QTc should be based on single or averaged QTc values of triplicate electrocardiograms obtained over a brief (e.g., 5-10 minute) recording period.

A participant who meets the bulleted criteria based on the average of triplicate ECG readings will be withdrawn from study treatment:

- QTc >500 msec OR Uncorrected QT >600 msec
- Change from baseline of QTc >60 msec

For participants with underlying bundle branch block, follow the discontinuation criteria listed below:

- Baseline QTc with Bundle Branch Block <450 msec, Discontinuation QTc with Bundle Branch Block >500 msec
- Baseline QTc with Bundle Branch Block <450-480 msec, Discontinuation QTc with Bundle Branch Block ≥530 msec.

See the SoA for data to be collected at the time of early withdrawal (EW visit) and follow-up and for any further evaluations that need to be completed.

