12.7. Appendix 7: Liver Safety: Required Actions and Follow-up Assessments

Phase II liver chemistry stopping and increased monitoring criteria have been designed to assure participant safety and evaluate liver event etiology

Phase II liver chemistry stopping criteria and required follow up assessments

Liver Chemistry Stopping Criteria				
ALT-absolute	ALT ≥ 5xULN	ALT ≥ 5xULN		
ALT Increase	ALT ≥ 3xULN persists for ≥4 weeks			
Bilirubin ^{1, 2}	ALT $\geq 3xULN$ and bilirubin $\geq 2xUL$.N (>35% direct bilirubin)		
INR ²	ALT ≥ 3xULN and INR>1.5, if INR	measured		
Cannot Monitor	ALT ≥ 3xULN and cannot be monitored	ed weekly for 4 weeks		
Symptomatic ³	ALT ≥ 3xULN associated with syn related to liver injury or hypersensi	nptoms (new or worsening) believed to be tivity		
	Required Actions and Follo	w up Assessments		
	Actions	Follow Up Assessments		
• Immediately	discontinue study treatment	Viral hepatitis serology ⁴		
 Report the event to GSK within 24 hours Complete the liver event CRF and complete an SAE data collection tool if the event also meets the criteria for an SAE² 		 Obtain INR and recheck with each liver chemistry assessment until the transaminases values show downward trend. 		
Perform liver chemistry event follow up assessments		 Obtain blood sample for pharmacokinetic (PK) analysis within 1 week after the liver event⁵ 		
Monitor the participant until liver chemistries resolve, stabilize, or return to within baseline (see MONITORING below)		Serum creatine phosphokinase (CPK) and lactate dehydrogenase (LDH).		
Do not restart/rechallenge participant with study treatment unless allowed per protocol and GSK Medical Governance approval is granted (see below)		 Fractionate bilirubin, if total bilirubin≥2xULN 		
		Obtain complete blood count with differential to assess eosinophilia		
If restart/rechallenge not allowed per protocol or not granted, permanently discontinue study treatment and continue participant in the study for any protocol specified follow up assessments		 Record the appearance or worsening of clinical symptoms of liver injury, or hypersensitivity, on the AE report form Record use of concomitant medications 		

MONITORING:

For bilirubin or INR criteria:

- Repeat liver chemistries (include ALT, AST, alkaline phosphatase, bilirubin) and perform liver event follow up assessments within 24 hrs
- Monitor participants twice weekly until liver chemistries resolve, stabilize or return to within baseline

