- A specialist or hepatology consultation is recommended

For All other criteria:

- Repeat liver chemistries (include ALT, AST, alkaline phosphatase, bilirubin) and perform liver event follow up assessments within 24-72 hrs
- Monitor participants weekly until liver chemistries resolve, stabilize or return to within baseline

- on the concomitant medications report form including acetaminophen, herbal remedies, other over the counter medications.
- Record alcohol use on the liver event alcohol intake case report form (CRF) page

For bilirubin or INR criteria:

- Anti-nuclear antibody, anti-smooth muscle antibody, Type 1 anti-liver kidney microsomal antibodies, and quantitative total immunoglobulin G (IgG) or gamma globulins.
- Serum acetaminophen adduct high performance liquid chromatography (HPLC) assay (quantifies potential acetaminophen contribution to liver injury in participants with definite or likely acetaminophen use in the preceding week [James, 2009]). NOTE: not required in China
- Liver imaging (ultrasound, magnetic resonance, or computerised tomography) and /or liver biopsy to evaluate liver disease; complete Liver Imaging and/or Liver Biopsy CRF pages.
- Serum bilirubin fractionation should be performed if testing is available. If serum bilirubin fractionation is not immediately available, discontinue study treatment for that subject if ALT ≥ 3xULN and bilirubin ≥ 2xULN.. Additionally, if serum bilirubin fractionation testing is unavailable, record presence of detectable urinary bilirubin on dipstick, indicating direct bilirubin elevations and suggesting liver injury.
- 2. All events of ALT ≥ 3xULN and bilirubin ≥ 2xULN (>35% direct bilirubin) or ALT ≥ 3xULN and INR>1.5, if INR measured which may indicate severe liver injury (possible 'Hy's Law'), must be reported as an SAE (excluding studies of hepatic impairment or cirrhosis); INR measurement is not required and the threshold value stated will not apply to participants receiving anticoagulants
- New or worsening symptoms believed to be related to liver injury (such as fatigue, nausea, vomiting, right upper quadrant pain or tenderness, or jaundice) or believed to be related to hypersensitivity (such as fever, rash or eosinophilia)

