- 4. Includes: Hepatitis A IgM antibody; Hepatitis B surface antigen (HbsAg) and Hepatitis B Core Antibody (IgM); Hepatitis C RNA; Cytomegalovirus IgM antibody; Epstein-Barr viral capsid antigen IgM antibody (or if unavailable, obtain heterophile antibody or monospot testing); Hepatitis E IgM antibody
- 5. PK sample may not be required for participants known to be receiving placebo or non-GSK comparator treatments.) Record the date/time of the PK blood sample draw and the date/time of the last dose of study treatment prior to PK blood sample draw on the CRF. If the date or time of the last dose is unclear, provide the participant's best approximation. If the date/time of the last dose cannot be approximated OR a PK sample cannot be collected in the time period indicated above, do not obtain a PK sample. Instructions for sample handling and shipping are in the SRM.

Phase II liver chemistry increased monitoring criteria with continued therapy

Liver Chemistry Increased Monitoring Criteria – Liver Monitoring Event				
Criteria	Actions			
ALT ≥3xULN and <5xULN and bilirubin <2xULN, without symptoms believed to	Notify the GSK medical monitor within 24 hours of learning of the abnormality to discuss participant safety.			
be related to liver injury or	Participant can continue study treatment			
hypersensitivity, and who can be monitored weekly for 4 weeks	Participant must return weekly for repeat liver chemistries (ALT, AST, alkaline phosphatase, bilirubin) until they resolve, stabilise or return to within baseline			
	If at any time participant meets the liver chemistry stopping criteria, proceed as described above			
	If, after 4 weeks of monitoring, ALT <3xULN and bilirubin <2xULN, monitor participants twice monthly until liver chemistries normalize or return to within baseline.			

References

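### Section 8.1.1 leaves the liver stop to the investigator's consideration without separating stopping from monitoring-only conditions; for the stopping conditions this conflicts with the mandatory stop in Section 8.1 and Appendix 7

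*Protocol*

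**What the plan says.** All the text below is from the current version of the protocol, which comes first in a file that also contains superseded versions.

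- **Section 8.1, Discontinuation of Study Treatment.** The list of stopping criteria opens with "A participant must be withdrawn from study treatment if any of the following stopping criteria are met". Item 1, for liver chemistry, is "Meets any of the protocol-defined liver chemistry stopping criteria".
- **Section 8.1.1, Liver Chemistry Stopping Criteria.** After a paragraph on how the stopping and increased-monitoring criteria were designed, it states "Discontinuation of study treatment for abnormal liver tests should be considered by the investigator when a participant meets one of the conditions" in the algorithm, "or if the investigator believes that it is in the best interest of the participant". The algorithm is titled as one for both stopping and increased monitoring.
- **Appendix 7 (Section 12.7), stopping tier.** The first required action is "Immediately discontinue study treatment". Footnote 1 covers ALT of at least 3xULN with bilirubin of at least 2xULN: "If serum bilirubin fractionation is not immediately available, discontinue study treatment for that subject".
- **Appendix 7, increased-monitoring tier.** For ALT of at least 3xULN but below 5xULN, bilirubin below 2xULN, no attributable symptoms and weekly monitoring feasible: "Participant can continue study treatment". If a stopping criterion is met later, the stopping actions apply.
- **Section 8.1.3.1.** Restart is barred once liver stopping criteria have been met.

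**The concern.** A stopping rule should have the same force wherever it is stated. Here one event, meeting a liver stopping criterion, compels a stop in Section 8.1 and Appendix 7 but only prompts consideration in Section 8.1.1. An investigator who considers stopping, decides against it and gives the next infusion has complied with Section 8.1.1 and breached the other two. Section 8.1.1 is also the subsection headed for exactly this event.

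What is at stake is participant safety and the consistency of protocol-deviation handling, in the first study of this antibody by this sponsor. No estimate or test depends on it.

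**Working it through.** The plan gives no figure to reproduce, so the check is a comparison of texts.

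**Step 1: does the discretionary verb reach the algorithm conditions?** The Section 8.1.1 sentence has two limbs. The first is triggered by meeting an algorithm condition. The second, "or if the investigator believes that it is in the best interest of the participant", is triggered by the investigator's own judgement. Because judgement has a limb of its own, the verb in the first limb governs the algorithm conditions themselves.

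**Step 2: which conditions are these?** By its title the algorithm contains both tiers. The sentence does not separate them, so each tier has to be tested.

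| Condition | Section 8.1, item 1 | Appendix 7 | Section 8.1.1 sentence | Consistent? |
|---|---|---|---|---|
| Stopping criterion, e.g. ALT of at least 5xULN | Withdrawal compulsory | Immediate discontinuation | Stop to be considered | No |
| ALT of at least 3xULN, bilirubin of at least 2xULN, fractionation not immediately available | Withdrawal compulsory (footnote 1 applies the bilirubin criterion) | Discontinue | Stop to be considered | No |
| Increased-monitoring criteria only | Not triggered | May continue, with weekly chemistry | Stop to be considered | Yes |

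The conflict is confined to the stopping tier.

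**Step 3: is this simply how the protocol words its stopping rules?** Section 8.1.2, the only other criterion-specific subsection, says "A participant who meets the bulleted criteria based on the average of triplicate ECG readings will be withdrawn from study treatment". So the softer verb is not a general convention. This comparison carries limited weight, because the QTc rule has no monitoring-only tier.

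**Step 4: could dosing actually continue?** Infusions are scheduled at Weeks 0, 4, 8 and 12, four in all. Clinical chemistry is drawn at Week 2 among other visits. A participant who met a stopping criterion at Week 2 would have 4 − 1 = 3 infusions still scheduled. That is the most that could follow for one participant if Section 8.1.1 were read alone.

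**Step 5: is the mandatory rule otherwise firm?** Yes. Three statements order the stop: Section 8.1 item 1, the Appendix 7 required action and Appendix 7 footnote 1. Section 8.1.3.1 fits them, since a bar on restart presupposes a stop. The Section 8.1.1 sentence is the outlier.

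**The case against.** The best defence is that the triggers differ. Section 8.1 and Appendix 7 speak of stopping criteria, while Section 8.1.1 speaks of abnormal liver tests and of conditions in an algorithm that also contains a monitoring tier. For a mixed set a permissive verb can serve as an umbrella, with Section 8.1 and Appendix 7 fixing which members compel a stop. This stands for the monitoring tier, and it is why the sentence cannot simply be turned into an unqualified order to stop. It does not rescue the stopping tier. The sentence makes no distinction, and it sits under a heading that names only stopping criteria.

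A second defence is that the current flowchart is not reproduced in the text at hand and may settle the matter. The flowchart text that survives in the superseded original version of the protocol has separate endpoints for continuing and for discontinuing. If the current one is similar, it orders the stop, but the sentence introducing it is then still too weak. The point does not rest on the figure.

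A third defence is practical. Section 8.1.1 falls under the compulsory list in Section 8.1 and sends the reader to Appendix 7, which a site needs anyway for follow-up tests and reporting. This stands, and it keeps the point small.

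A reader might infer more than the text supports:

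- **That the sentence is the opening instruction for a liver event.** It is not. It follows a paragraph on the design of the criteria.
- **That the number of participants harmed can be estimated.** Assuming that 0.5% to 2% of the 148 randomized participants meet a criterion gives 148 × 0.005 = 0.74 to 148 × 0.02 = 2.96. But that rate is not in the protocol, and the product counts everyone who meets a criterion. It does not count those wrongly kept on drug because a site followed one sentence against two other parts of the protocol. The protocol offers no basis for that probability.

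**Conclusion.** The point holds as a minor safety-wording error. For the stopping conditions, Section 8.1.1 gives the liver stop less force than Section 8.1 item 1 and Appendix 7. For the monitoring-only conditions there is no conflict.

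The practical effect is small because the mandatory rule can be recovered from the other two places. The protocol does not, taken as a whole, leave the liver stop to the investigator, and it should not be described that way. No count of affected participants can be derived. The ceiling for one participant is three further infusions, and that requires a site to read Section 8.1.1 in isolation. Sample size, power and the primary analysis are unaffected.

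The conclusion rests only on the current wording of Sections 8.1 and 8.1.1 and Appendix 7. It makes no assumption about event rates or about the content of the current flowchart.

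**What to change.** Replace the Section 8.1.1 sentence with one that separates the cases, for example:

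*Study treatment must be discontinued when a participant meets any liver chemistry stopping criterion in the algorithm or Appendix 7. Participants who meet only the increased-monitoring criteria may continue as described in Appendix 7. The investigator may also discontinue study treatment at any time if this is in the participant's best interest.*

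This keeps the monitoring tier and the investigator's discretion, which Section 8.1 already allows, and brings the stopping tier into line with the rest of the protocol. The cost is one sentence of protocol wording, with no change to design, data collection or analysis.
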